7.9 Pregnancy

Should study personnel become aware of a subject's (or subject's partner's) pregnancy, the site personnel must report the pregnancy to the Sponsor's medical monitor within 24 hours by using the pregnancy notification form. The female subject will discontinue Study drug. The pregnancy will be followed until the outcome is known and will be reported to the Sponsor.

8 STUDY OR SITE TERMINATION AND SUBJECT DISCONTINUATION

8.1 Subject Discontinuation

Subjects are encouraged to complete the study; however, they may voluntarily withdraw at any time. The investigator will provide a written explanation of the reason for discontinuation in a source document and this information will also be recorded on the appropriate eCRF page. If a subject withdraws before completion, every effort should be made to complete the Day 84 assessments scheduled during the End of Study visit.

A subject may be removed from the study for the reasons described in Section 8.1.1 through Section 8.1.5.

8.1.1 Adverse Event

If a subject experiences an AE that, in the judgment of the investigator, the sponsor, or the medical monitor, presents an unacceptable consequence or risk to the subject, the subject may be discontinued from the study.

8.1.2 Intercurrent Illness

A subject may be discontinued from the study if, in the judgment of the investigator, the subject develops an intercurrent illness or complication that is not consistent with the protocol requirements or that, in any way, justifies withdrawal from the study.

8.1.3 Noncompliance

After the investigator, the medical monitor and/or study monitor consult (and the sponsor if appropriate), a subject may be discontinued from the study for the following administrative reasons:

Failure to receive study medication or treatment as mandated by the specific instructions provided in Section 5

Failure to comply with protocol requirements

8.1.4 Refusal of Investigational Product Administration

Any subject refusing clinical trial material for any reason will be discontinued from the study, and the reason(s) for their discontinuation will be documented on the appropriate eCRF page. Reasonable efforts should be made to monitor the subject for AEs and to complete follow-up assessments after treatment discontinuation. These efforts should be documented on the appropriate eCRF page.

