It can sometimes be challenging to determine if a wart is completely clear after treatment due to ongoing local skin reactions. At any visit where the investigator is unable to evaluate or treat some warts due to ongoing local skin reactions, an "Unscheduled" Visit should be documented. The timing of the next visit will be determined by the resolution of the local skin reaction. A Treatment Visit should be documented at every visit where Study drug is applied. Treatment should only take place at a visit when all warts are evaluable (i.e., not obscured by an ongoing LSR) and all warts that are not completely clear, should undergo treatment with Study drug. No partial treatment of warts is permitted.

For Cohort 2, Study drug is to be applied to the wart site on any Treatment Visit where a new clinical assessment of complete clearance is made for that wart (*e.g., if a patient returns for Treatment Visit 2 and is clinically assessed to have no visible evidence of remaining wart, then Study drug is to be applied to this wart site at Treatment Visit 2. However, if the patient remains completely clear at that wart site when returning for Treatment Visit 3, then no Study drug would be applied at Treatment Visit 3.*) Should it become clear that the subject will be unable to complete the EOS visit within the allowed window of Day 84 (- 0/+ 8) days, the subject should be brought in for their EOS visit as soon as they are able. This will be documented as a protocol deviation.

In instances where the clinician can adequately assess the treatment sites but is uncertain if residual wart is remaining, treatment should be applied, and the subject should return for evaluation per protocol. Treatment visits and assessments are to take place in order (e.g., Treatment 1, Treatment 2, Treatment 3 and Treatment 4). Subjects that receive fewer than 4 treatments within the 63-day (Cohort 1) or 75-day (Cohort 2) treatment period, due to the duration of post-treatment local skin reactions, will not be considered a protocol deviation. No treatment should be administered after the 63-day treatment period in Cohort 1 or the 75-day treatment period in Cohort 2 without Sponsor's approval.

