assessments with the research team member. Should a subject report experiencing excessive blistering, ulceration, edema, pain or another adverse event needing physician assessment, they will be scheduled for an “Unscheduled” study visit and safety evaluation as soon as possible.

- Medical history, vital signs, and physical examinations:
 - Medical history, wart history, Fitzpatrick Skin Type and limited physical exams will be collected for each subject. A limited physical examination will be completed before the first treatment and at the EOS visit. Vital signs (temperature and heart rate) will be obtained before the treatment is applied at each visit and at the start of the Day 84 (EOS) Visit. Additional physical examinations will be performed when clinically warranted (e.g., subject reports symptoms classified as an AE requiring further evaluation).
- Limited physical examinations will be performed by a qualified medical practitioner at screening and at EOS visits. Height and weight will be recorded at the screening visit and at the EOS Visit. Unscheduled physical examinations will be performed when clinically warranted (e.g., if a subject reports signs or symptoms requiring further evaluation).
- Vital signs (e.g., heart rate and temperature) will be obtained at all Treatment Visits prior to treatment. A final assessment of vital signs will be obtained at the EOS Visit.
- If the subject discontinues the study prematurely (after the first treatment) for any reason, attempts will be made to encourage the subject/guardian to complete the EOS assessments.
- Subjects will be monitored for signs and symptoms of AEs throughout the study. All AEs (including LSRs) will be reported on the source and in the electronic case report form (eCRF), including seriousness, severity, action taken, and relationship to the Study drug. If AEs should occur, the first concern will be the safety of the subject.

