Subjects who receive all 4 planned treatments of VP-102 (e.g., up to four treatments within the 75-day treatment window or cleared of all treatable warts prior to Day 75), are assessed for clearance at the EOT visit, and have no major protocol violations, will be included in the Per Protocol population. Major protocol deviations will be evaluated prior to excluding subjects from the per Protocol population. Major deviations will be determined via a clinical review of all deviations; criteria for major deviations include the following:

- Failure to obtain informed consent;
- Informed consent was incorrect or incomplete;
- Non-compliance with inclusion/exclusion criteria;

- IP administration/dosing errors;
- Non-compliance with study protocol procedures;
- Unreported serious adverse events.

In addition, the following pre-determined reasons will exclude subjects from being included in the Per Protocol population:

- Subjects who do not come in for required treatment visits
- Subjects who do not return for the EOT study visit
- Subjects who refuse to have all of their treatable warts treated or investigators who refuse to treat all treatable warts
- Early removal of the study drug not associated with pain, blistering or other medically appropriate reason for early removal. Early removal will be determined by the defined study window of 24 hrs +/- 8 hrs.
- Subjects who begin alternative treatments for their warts after starting the study
- Subjects enrolled who did not meet the inclusion/exclusion criteria

Safety Population:

The Safety population will include subjects who receive at least one treatment of VP-102.

7. Study Population

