8.4.1. Handling of Missing Data for Complete Clearance Endpoint

The efficacy endpoint, proportion of subjects exhibiting complete clearance of all treatable warts, is to be assessed during the study. Assessments are to be done at Treatment Visit 2, Treatment Visit 3, Treatment Visit 4, the EOT visit and follow-up visits at Day 105, Day 126 and Day 147.

Subjects who do not have an assessment of complete clearance of all treatable warts in a particular visit window for any of the scheduled assessments will be considered to have missing data for this endpoint at that visit. The primary method to handle missing data will be to assign all subjects with missing clearance data as not having achieved complete clearance. For additional considerations related to assessments of clearance, see Section 8 (Efficacy Analysis).

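### Refusing study drug takes a subject off study, which puts the Day 84 reading at risk and leaves its scoring unsettled

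*Protocol*

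**What the plan says.** **Refusal.** Protocol Section 8.1.4: "Any subject refusing clinical trial material for any reason will be discontinued from the study". The same section continues: "Reasonable efforts should be made to monitor the subject for AEs and to complete follow-up assessments after treatment discontinuation". The neighbouring grounds for removal (adverse event in 8.1.1, intercurrent illness in 8.1.2, noncompliance in 8.1.3) are all discretionary. Section 8.1.3 includes not receiving study medication as instructed, which is close to the same event.

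**Final assessments after leaving.** Section 8.1: "every effort should be made to complete the Day 84 assessments scheduled during the End of Study visit". Section 4.3.1, for premature discontinuation: "attempts will be made to encourage the subject/guardian to complete the EOS assessments".

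**Scoring.** SAP Section 8.4.1 (Cohort 2) will "assign all subjects with missing clearance data as not having achieved complete clearance", where missing means no assessment in the visit window. SAP Section 8 sets the EOT window at Day 74 to Day 94. Protocol Section 9.2.7 has the equivalent rule for both cohorts, without that window. Protocol Section 8.2 states that a subject who does not complete the study counts as a failure for the primary endpoint. SAP Section 7.1 defines study completion as having completed the Day 147 visit. Protocol Section 4.4 and SAP Section 8.4 treat a subject who asks to leave because of study-related adverse events or spreading disease as a treatment failure.

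**Drug at a clear site (Cohort 2).** Section 4.1: "Study drug is to be applied to the wart site on any Treatment Visit where a new clinical assessment of complete clearance is made". SAP Section 3 repeats this.

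**The concern.** Section 8.1.4 merges two events that the primary analysis needs to keep apart: stopping the drug and leaving the study. Section 7.9 does separate them, since a pregnant subject stops drug and nothing is said about leaving the study. Under 8.1.4 a subject who declines drug is formally off study, and from then on the Day 84 reading depends on a best-efforts request.

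The primary endpoint is clearance at Day 84 in all enrolled subjects. If refusers who are clear at Day 84 are scored as failures, the rate partly measures willingness to accept a further application. Refusal is unlikely to be random: pain, blistering or apparent clearance are all plausible reasons. The synopsis says the clearance rates are meant to inform assumptions for later placebo-controlled trials, so a downward bias would carry forward. In Cohort 2 the same subjects may also be missing from the durability follow-up at Days 105, 126 and 147.

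**Working it through.** **1. Is the Day 84 reading lost by rule?** No. Sections 8.1.4, 8.1 and 4.3.1 all ask for follow-up or final assessments. The requests are imprecise for Cohort 2, however:
- Section 8.1 names Day 84 but attaches it to the End of Study visit, and Section 4.3.1 names only EOS. In Cohort 2, Day 84 is the EOT visit, and the Table 2 footnotes place EOS at Day 147.
- Section 8.1.4 names no visits. None of the three lists Day 105 or Day 126.
- None fixes when a discontinued subject should be seen.

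**2. What if the last assessment is made at the time of refusal?** The SAP's planned days after the first treatment are 21, 42 and 63. The EOT window opens on Day 74, which is 53, 32 and 11 days later. A reading taken at refusal on any of these days lies outside the window, so SAP 8.4.1 scores the subject as not cleared at EOT. Only a visit delayed to Day 74 or later would count.

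**3. What if an in-window reading of clear is obtained (Cohort 2)?**
- Protocol 9.2.7 and SAP 8.4.1: the reading is not missing, so the subject is cleared.
- Protocol 8.2 with SAP 7.1, read literally: no Day 147 visit means not a completer, so the subject is a failure. This would also fail a subject who is clear at Day 84 and simply misses Day 147.
- Protocol 4.4 and SAP 8.4: if the subject asked to leave because of adverse events or spreading disease, a treatment failure.

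The documents do not say which rule governs.

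**4. Which subjects are exposed?** In Cohort 2, a subject whose site has just been judged clear can be asked to accept drug once more (4.1), and declining falls under 8.1.4. Other text points the other way: the visit lists in the synopsis and Section 6.1 tie application to remaining warts, and SAP Section 8 plans treatment while warts are present. Those passages need reconciling. In Cohort 1, subjects who clear before Treatment Visit 4 move to phone calls with no application due (4.1), so only refusers who clear later are affected.

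**5. Size.** There is no figure in the plan to reproduce: no refusal rate, clearance rate or power calculation is given. The inputs are about 35 enrolled in Cohort 2 and about 20 completing EOS in Cohort 1 (Protocol 9.2.6), with ITT as all enrolled (9.2.2).
- Shift per clear refuser scored as a failure = 1/N.
- Cohort 2: 1/35 = 2.9 points.
- Cohort 1: a refuser who does not complete EOS is additional to the 20 completers, so N is at least 21 and the shift is at most 1/21 = 4.8 points.

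Illustration for Cohort 2, assuming 18 clear: 18/35 = 51.4% (exact 95% CI 34.0 to 68.6). With two clear refusers scored as failures: 16/35 = 45.7% (28.8 to 63.4).

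Expected shift = r × c × m, where r is the refusal rate, c the share of refusers clear at Day 84, and m the share of those scored as failures. All three are assumptions; r = 3% to 15% and c = 30% to 80% are used here.
- m = 1: from 0.03 × 0.30 = 0.9 points to 0.15 × 0.80 = 12.0 points.
- m = 0.5: 0.45 to 6.0 points.
- m = 0 (every reading obtained and used): 0 points.

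**6. Consistency between endpoints.** SAP 8.4.2 carries the last wart count forward, while 8.4.1 scores missing clearance as failure. A Cohort 2 subject with no warts at Treatment Visit 2 who declines drug and has no later reading would show a 100% wart reduction and be not cleared at the same EOT visit.

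**The case against.** The strongest reply is that the protocol already asks for the missing reading in three places, so a well-run site would obtain it and the shift would be zero. This stands against a stronger reading that a reader might infer, namely that Section 8.1.4 itself deprives a clear subject of the Day 84 assessment and makes that subject a failure. The documents do not say so; loss of the reading is a risk. The reply does not deal with the EOS wording in Cohort 2, assessments brought forward before Day 74, or the failure rule in 8.2.

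A reader might also take the Per Protocol exclusion, "Subjects who refuse to have all of their treatable warts treated or investigators who refuse to treat all treatable warts" (Protocol 9.2.2, SAP Section 6), as showing that refusers are expected to stay in the study. It does not: the same list excludes subjects who never return for the final visit, so it is compatible with 8.1.4. Nor is safety information necessarily lost, since 8.1.4 asks for adverse event monitoring and Sections 7.1 and 7.8 require follow-up of unresolved events.

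For subjects who ask to leave because of adverse events or spreading disease, failure scoring is a stated choice rather than a side effect. That is fair, and it is why this rule has to be kept or dropped explicitly. The failure sentence in 8.2 sits under study and site termination and may have been meant only for that setting, but nothing in it says so.

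Finally, the study is descriptive and small: a 2.9-point shift is minor beside an interval of roughly ±17 points at N = 35. True, but the shift is a bias in one direction and can be avoided by wording.

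**Conclusion.** The point holds as a risk and an unresolved scoring conflict. Removal from the study on refusal is mandatory under 8.1.4 and at odds with the rest of that section and with 8.1.1 to 8.1.3. A refuser with no usable Day 84 reading is scored as not cleared, and the documents give conflicting answers for one whose in-window reading is clear.

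The size is 2.9 points per affected subject in Cohort 2. In Cohort 1 it is at most about 4.8 points, on the assumption that the refuser is additional to 20 completers. The number of such subjects is unknown, and if all readings are obtained and used the effect is nil. The case of a subject already clear when declining concerns Cohort 2 only, and depends on how the instructions for newly clear sites are reconciled. The change is worth making because it is cheap and protects the primary estimate; the matter does not invalidate the design.

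**What to change.** Reconcile Protocol 4.3.1, 4.4, 8.1, 8.1.4, 8.2 and 9.2.7 with SAP 8.4 and 8.4.1, leaving every dosing and treatment-stopping rule as it is:

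1. Record discontinuation of study drug separately from discontinuation of the study.
2. Keep subjects who stop drug without withdrawing consent on the assessments already scheduled: Day 84 in both cohorts, and Days 105, 126 and 147 in Cohort 2. Name EOT as well as EOS where final assessments are requested.
3. Use an observed in-window Day 84 result for the ITT primary endpoint, and limit the not-cleared rule to missing assessments. Amend 8.2 to agree, so that missing Day 147 does not overturn a Day 84 result.
4. State whether the treatment-failure rule for subjects who ask to leave because of adverse events or spreading disease stands as an exception.
5. Leave the Per Protocol exclusion unchanged.

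The cost is a wording amendment to both documents and a separate data field for stopping drug if the case report form lacks one. No new visits are added. The downside is that some subjects will attend visits without receiving treatment.

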8.1.5 Withdrawal of Consent

Any subject who withdraws consent for any reason at any time during the study will be discontinued from the study, and the reason(s) will be documented on the appropriate source and eCRF page. If subjects do not want their data that has already been submitted or specimens utilized, they will need to submit a request in writing to the Investigator for removal of their information.

8.2 Premature Study or Site Termination

If the Sponsor, investigator, medical monitor, study monitor, or appropriate regulatory officials discover conditions arising during the study that indicate that the study should be halted or that the site should be terminated, this action may be taken after appropriate consultation among the Sponsor, investigator, medical monitor, and study monitor. Conditions that may warrant termination of the study include, but are not limited to, the following:

- The discovery of an unexpected, serious, or unacceptable risk to the subjects enrolled in the study
- A decision on the part of the Sponsor to suspend or discontinue testing, evaluation, or development of the product
- A study conducted at a single site in a multicenter study may also warrant termination under the following conditions:
 - Failure of the investigator to enroll subjects into the study at an acceptable rate
 - Failure of the investigator to comply with pertinent regulations of appropriate regulatory authorities
 - Submission of knowingly false information from the site to the sponsor, study monitor, or appropriate regulatory authority
 - Insufficient adherence to protocol requirements

Study termination and follow-up will comply with the conditions set forth in International Council for Harmonisation (ICH) E6, Guideline for Good Clinical Practice. Data from all sites, including those that have been terminated for non-compliance or unsatisfactory enrollment will be evaluated and included in the interpretation of study findings. Subjects from sites that terminate early will be considered for analysis. If a subject does not complete the study, they will still be counted as a failure for the primary endpoint.

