This is an open-label study where all subjects are to receive the Study drug. The study will enroll to treat a minimum of 20 subjects, 2 years of age and older, presenting with 1-6 common warts with the goal of approximately 20 subjects completing all study activities in Cohort 1 per protocol. Cohort 2 will utilize up to 4 sites to enroll approximately 35 subjects (12 years and older). Although no formal power calculations have been performed, it is expected that a sample size of 20 subjects (Cohort 1) and 35 subjects (Cohort 2) evaluable at the EOS/EOT visit (Day 84 for both Cohorts) will be informative regarding wart clearance rates that can support assumptions in subsequent placebo-controlled trials. A sample size of 20 completed subjects for Cohort 1 and approximately 35 subjects for Cohort 2, will provide information to build an adequate safety profile of VP-102 in common warts. The primary analysis will be conducted at Day 84 for both Cohorts. The final analysis will be conducted for Cohort 2 when the last patient has completed the visit on Day 147.

Subjects who receive all planned treatments of VP-102 (e.g., up to four treatments within the 63 day treatment window, or cleared of all treatable warts prior to Day 63 in Cohort 1; and in Cohort 2 complete up to four treatments within the Day 75 treatment window or clear prior to Day 75) and have no major protocol violations are assessed for clearance at the EOS visit and included in the Per Protocol population.

Subject demographics, efficacy tables and subject dropout rates will be tabulated at the end of the study. Data will be summarized using descriptive statistics (sample size, mean, median, standard deviation, minimum, maximum) for continuous variables and frequencies and percentages for discrete variables. Corresponding by-subject data listings will be tabulated.

Adverse events, including local skin reactions, will be coded with the MedDRA® dictionary. The number and percentage of subjects having treatment-emergent AEs will be tabulated by system organ class and MedDRA preferred term with a breakdown by treatment group.

Table 1 Study Schedule of Assessments and Procedures – Cohort 1

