Subjects in Cohort 1 that achieve complete clearance of all treatable warts prior to Treatment Visit 4, will receive ERT phone calls at the required 2-week treatment intervals to assess the status of any AEs or skin reactions since the last visit and confirm there has been no recurrence or development of new warts. In the event warts are present, the subject will be scheduled for a Treatment Visit per protocol. (*Consider calling the subject a few days prior to the 2-week interval (e.g., 11 or 12 days) to ensure adequate time for scheduling assessment and treatment if needed.*)

Subjects participating in Cohort 2, will be required to attend all visits regardless of whether they have achieved complete clearance of all warts at a previous visit. At these visits, Study drug application is not required if the warts have been clear for at least one follow up visit

and the investigator determines that additional treatment is not needed. Subjects participating in Cohort 2, that have completed their Day 84 EOT visit (- 0/+ 8 days), will be assessed at 3 additional follow-up visits conducted at Day 105, Day 126 and Day 147.

Subjects in Cohort 1 who are not assessed as 100% cleared of all treatable lesions at the Day 84, (EOS) visit will have completed the study and will be further treated per standard of care at their physician's discretion but may not be re-enrolled in this study. Subjects in Cohort 2 who are not assessed as 100% cleared of all treatable lesions at the Day 147; (EOS) visit will have completed the study and will be further treated per standard of care at their physician's discretion but may not be re-enrolled in this study

All subjects will receive application of the Study drug (VP-102) to common warts including a 1-2 mm margin of healthy, surrounding skin with an interval of at least 14 days in Cohort 1, and every 21 days in Cohort 2, until complete clearance of all treatable warts, or a maximum of 4 applications. Warts are to be treated and then occluded with transparent surgical tape (e.g.; 3M™ Blenderm™ brand) that will remain on overnight and removed just prior to the 24-hour ERT phone call.

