9.2.7 Handling of Missing data

Clearance of all treatable warts is to be assessed at each Treatment Visit as well as unscheduled visits over the duration of the study. The assessment done at the EOS Visit (Day 84) will be considered to be the primary efficacy endpoint.

Subjects who do not have an assessment of complete clearance of all treatable warts at the EOS Visit (Day 84) will be considered to have missing data for the primary endpoint. The primary method to handle missing data will be to assign all subjects with missing complete clearance data as not having achieved complete clearance.

The procedures for handling missing data for other study endpoints will be described in the statistical analysis plan.

9.3 Informed Consent/Assent and Authorization for Use and Disclosure of Protected Health Information

Written assent and informed consent and authorization of use and disclosure of protected health information must be obtained from each subject (or the subject's legally acceptable representative) before performing any study-specific screening/baseline period evaluations. One copy of the signed informed consent form (and IRB-required assent form) and authorization for use and disclosure of protected health information form will be given to the subject, and the investigator will retain the original. The informed consent/assent form and authorization for use and disclosure of protected health information, which is prepared by the investigator or the site, must have been reviewed and approved by the sponsor, the study monitor, and the investigator's IRB and privacy board (if separate from the IRB) before the initiation of the study. The informed consent form must contain the 20 elements of informed

consent described in International Council for Harmonisation E6, Section 4.8. The authorization for use and disclosure of protected health information must contain the elements required by Title 45 of the Code of Federal Regulations, Section 164.508(b), and any local regulations for valid authorizations.

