7.1. Subject Disposition

Information regarding subject disposition will be summarized for all subjects. Summaries will include: number of subjects in each analysis population, number of subjects who completed the treatment phase of the study, number of subjects assessed for clearance at the End of Treatment Visit (EOT), number of subjects completing the study, and number of subjects who discontinue the study early. Subjects will be considered to have completed the treatment phase of the study if they had a Day 84 (EOT) visit. In order for a subject to be considered to have completed the study, they must have completed their Day 147 visit. For those who discontinue early, the primary reason for early termination will be summarized.

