8.1. Efficacy Variables

Primary endpoint:

- Proportion of subjects exhibiting complete clearance of all treatable warts (baseline and new) at the End of Treatment (EOT) Visit (Day 84).

Secondary endpoints:

- Change from baseline in the number of treatable warts (baseline and new) at the EOT visit (Day 84).
- Change from baseline in the percent of treatable warts (baseline and new) at the EOT visit (Day 84).
- Proportion of subjects exhibiting complete clearance of all treatable warts (baseline and new) at Treatment Visit 2, Treatment Visit 3, Treatment Visit 4.

Exploratory endpoints:

- Percent reduction of all treatable warts (baseline and new) from baseline at Treatment Visit 2, Treatment Visit 3, Treatment Visit 4.
- Change from baseline in the number of treatable warts (baseline and new) at Treatment Visit 2, Treatment Visit 3, Treatment Visit 4.
- Proportion of subjects exhibiting $\geq 50\%$ clearance of all treatable warts (baseline and new) at the EOT visit as compared to baseline.
- Proportion of subjects who respond to treatment defined by a $\geq 50\%$ reduction in total wart area at EOT visit compared to baseline.
- Proportion of subjects exhibiting reduction of at least 1 treatable wart from baseline at Treatment Visit 2, Treatment Visit 3, Treatment Visit 4 and at the EOT Visit.
- Proportion of subjects exhibiting complete clearance of all treatable warts (baseline and new) at follow-up visits on Day 105, Day 126 and Day 147.
- Percent reduction of all treatable warts (baseline and new) from baseline at follow-up visits on Day 105, Day 126 and Day 147.
- Change from baseline in the number of all treatable warts (baseline and new) from baseline at follow-up visits on Day 105, Day 126 and Day 147.

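### Protocol 8.2 ties primary-endpoint failure to study completion (Day 147 in Cohort 2) and so contradicts the Day 84 missing-data rule in protocol 9.2.7 and SAP 8.4.1

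*Protocol*

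**What the plan says.** Protocol 8.2, at the end of the text on terminated sites, states: "If a subject does not complete the study, they will still be counted as a failure for the primary endpoint". It sets no time limit and makes no exception for a subject whose primary endpoint has already been assessed.

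For Cohort 2, SAP 7.1 separates two milestones. The first is the treatment phase: "Subjects will be considered to have completed the treatment phase of the study if they had a Day 84 (EOT) visit". The second is the study: "In order for a subject to be considered to have completed the study, they must have completed their Day 147 visit". Protocol 4.1 agrees on the second, saying that a Cohort 2 subject not fully clear at the "Day 147; (EOS) visit will have completed the study".

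The Cohort 2 primary endpoint is complete clearance at the EOT visit, Day 84 (protocol 4.3, SAP 8.1). On timing, the synopsis says: "The primary analysis will be conducted at Day 84 for both Cohorts". A final Cohort 2 analysis follows the last Day 147 visit.

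Protocol 9.2.7 treats the primary endpoint as missing only when there is no clearance assessment at Day 84, and then says: "The primary method to handle missing data will be to assign all subjects with missing complete clearance data as not having achieved complete clearance". SAP 8.4.1 applies the same principle visit by visit.

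Protocol 4.4 and SAP 8.4 add that a subject who asks to leave because of study-related adverse events or spreading disease is analysed as a treatment failure. Neither says whether this holds after Day 84.

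**The concern.** The 63 days between Day 84 and Day 147 are follow-up for durability, after the primary endpoint has been read. A rule that fails every non-completer makes the Day 84 result depend on attendance during those 63 days. The conflict is confined to Cohort 2 subjects assessed clear at Day 84 who leave, or whose site closes, before Day 147. In Cohort 1 the end of study is Day 84, so study completion and endpoint assessment coincide and the rules agree.

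For the affected subjects, 8.2 and the missing-data sections give different primary results from the same data, and 8.2 can only lower the rate. The synopsis says the clearance rates are meant to support assumptions for later placebo-controlled trials, so the figure carried forward should not depend on which section the analyst happened to read.

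**Working it through.** **Step 1: one subject under each rule.** Take a Cohort 2 subject assessed clear at Day 84 who has no Day 147 visit.

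| Source | What decides failure | Primary endpoint for this subject |
|---|---|---|
| Protocol 8.2 | Study not completed | Failure |
| Protocol 9.2.7 | No Day 84 clearance assessment | Clear |
| SAP 8.4.1 | No assessment in that visit's window | Clear at EOT; not cleared at Day 147 only |
| Protocol 4.4 and SAP 8.4 | Withdrawal for study-related adverse events or spreading disease, no time limit | Unsettled if that is the reason for leaving |

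The first row contradicts the second and third. The fourth leaves a related gap: even without 8.2, scoring after Day 84 is not fully fixed.

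**Step 2: size per subject.** The documents contain no power or precision calculation for Cohort 2, so there is no stated figure to reproduce. Planned enrolment is about 35. Each reclassified subject lowers the rate by 1/35 = 2.86, or 2.9 percentage points.

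**Step 3: illustration.** Assume 18 of 35 are clear at Day 84; this number is not in the documents. The intervals are exact (Clopper-Pearson) 95% limits.

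| Clear subjects leaving after Day 84 | Rate if 8.2 is applied | 95% interval |
|---|---|---|
| 0 (same as 9.2.7 and SAP 8.4.1) | 18/35 = 51.4% | 34.0 to 68.6 |
| 1 | 17/35 = 48.6% | 31.4 to 66.0 |
| 3 | 15/35 = 42.9% | 26.3 to 60.6 |
| 5 | 13/35 = 37.1% | 21.5 to 55.1 |

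**Step 4: range under stated assumptions.** Let p be the Day 84 clearance rate and d the loss between Day 84 and Day 147, independent of clearance. The expected understatement under 8.2 is p × d, and the chance that at least one of 35 subjects is affected is 1 − (1 − p × d)^35. The documents give neither p nor d. Assume p from 30% to 60% and d from 5% to 20%:

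- Low end: 0.30 × 0.05 = 1.5 points; chance of at least one, 41%.
- Middle: 0.50 × 0.10 = 5.0 points; chance of at least one, 83%.
- High end: 0.60 × 0.20 = 12.0 points; chance of at least one, 99%.

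**Step 5: the narrow reading of 8.2.** Suppose the sentence covers only terminated sites, and one of four sites closes between Day 84 and Day 147. With equal enrolment (35/4, about 9 subjects) and about half of them clear, 4 to 5 subjects are reclassified: 4/35 = 11.4 points to 5/35 = 14.3 points. Equal enrolment and half clear are assumptions. The step shows only that the narrow reading does not remove the conflict.

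**The case against.** The strongest reply is that the operative rule is already set. Protocol 9.2.7 is the dedicated missing-data section, SAP 8.4.1 matches it, and SAP 1 presents the SAP as the guide for the analysis. The 8.2 rule appears nowhere in protocol section 9 or in the SAP. This largely stands: an analyst working from the SAP would score the subject as clear. It does not remove the contradiction, because neither document gives the SAP precedence over 8.2, and 9.2.7 itself calls Day 84 the EOS visit, which for Cohort 2 it is not.

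Second, the sentence may have been meant only to keep subjects from terminated sites in the denominator. The location supports that; the wording does not limit it, and step 5 shows that the conflict survives.

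Third, SAP 7.1 defines completion for disposition counts, and protocol 4.4 ties dropout to the EOS/EOT assessment. If completion in 8.2 meant the EOT visit, 8.2 would agree with 9.2.7. That reading is possible, but 8.2 refers to the study, and protocol 4.1 places its end for Cohort 2 at Day 147.

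Three stronger inferences are tempting and should not be drawn:

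- **That the planned analysis is biased downward.** The SAP's planned analysis does not use 8.2; the bias arises only if 8.2 is followed.
- **That the primary result will change between the Day 84 and final analyses.** Day 147 completion may be unknown at the first, but nothing says the primary endpoint is re-scored at the second. The timing suggests, if anything, that 8.2 was not written with Day 147 in mind.
- **That losses in the earlier VP-102 studies (1 of 33, or 4 of 16 in one bridging cohort) size the effect.** Those were molluscum studies and whole-study losses. They say little about subjects already retained and clear at Day 84.

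**Conclusion.** The contradiction is real and lies in the text. For a Cohort 2 subject clear at Day 84 and lost before Day 147, protocol 8.2 gives failure while protocol 9.2.7 and SAP 8.4.1 give clearance, and no order of precedence is stated. The missing-data sections hold the rule that fits a Day 84 endpoint and would probably be followed, so this is a conflict to remove rather than evidence that the planned analysis is wrong.

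The supported size is 2.9 points per affected subject at 35 subjects. The 1.5 to 12.0 point range rests wholly on assumed clearance and loss. The study is open-label and descriptive, with no test or threshold at stake; what matters is that the Cohort 2 clearance rate has a single definition before it is used to plan later trials.

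**What to change.** Replace the sentence in protocol 8.2 with wording such as: *A subject without a clearance assessment at the Day 84 visit (Cohort 1 EOS, Cohort 2 EOT) is counted as not cleared for the primary endpoint. Leaving the study, or closure of the site, after an evaluable Day 84 assessment does not change the primary endpoint.*

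In the same edit, add to protocol 4.4 and SAP 8.4 that, for scoring the primary endpoint, the treatment-failure rule for withdrawals due to study-related adverse events or spreading disease applies only to withdrawals before the Day 84 assessment. Without this, the new 8.2 text would conflict with those two sections. Missing Day 105, 126 and 147 assessments remain handled at their own visits, as SAP 8.4.1 already provides.

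The cost is a short replacement in 8.2 and one clause each in protocol 4.4 and SAP 8.4. No additional data, visits or subjects are needed.
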